6.11.1. Co-Primary Outcome and Primary Analysis Methodology

The co-primary outcomes are:

- Proportion of patients achieving PASI 75
- Proportion of patients achieving sPGA (0,1)

The primary analysis will be based on the ITT Population for the Double-Blind Treatment Period (Period 2) comparing ixekizumab versus placebo at Week 12. The primary analysis is Fisher's exact test. Missing data will be imputed using the NRI method. The secondary analyses for the primary efficacy measures will be conducted using a logistic regression with treatment group, region, baseline sPGA score (severity of the Ps), and baseline weight category (<25kg; ≥25 to ≤50 kg; or >50 kg) as factors. Missing data will be imputed using the NRI method.

6.11.2. Gated Secondary Efficacy Analyses

The gated secondary outcomes are:

- Proportion of patients achieving PASI 90 at Week 12
- Proportion of patients achieving an sPGA (0) at Week 12
- Proportion of patients achieving PASI 100 at Week 12
- Proportion of subjects achieving ≥4-point improvement for subjects who had a baseline Itch NRS ≥4 at Week 12
- Proportion of patients achieving PASI 75 at Week 4
- Proportion of patients achieving sPGA (0,1) at Week 4

The gated secondary analyses will be based on ITT Population for the Double-Blind Treatment Period (Period 2) comparing ixekizumab versus placebo. The analysis will be Fisher's exact test. Missing data will be imputed using the NRI method.

6.11.3. Additional Analyses of the Co-Primary Outcome

There will be no adjustment for multiple comparisons for additional analyses of the co-primary outcomes.

To support the primary efficacy analysis, the co-primary outcomes, PASI 75 and sPGA (0,1), will be analyzed based on the PPS Population for the Double-Blind Treatment Period (Period 2), comparing ixekizumab versus placebo at Week 12 using Fisher's exact test with NRI.

6.11.4. Other Secondary Efficacy Analyses

There will be no adjustment for multiple comparisons for other secondary analyses.

The other secondary efficacy variables include:

- PASI 50, PASI 90, PASI 100, PASI change from baseline percent improvement

- sPGA (0)
- NAPSI change from baseline
- PSSI change from baseline
- PPASI change from baseline

The other secondary analyses for the Double-Blind Treatment Period (Period 2) will be based on the ITT Population, except (refer to [Table RHCD.6.4](#)):

- NAPSI: based on ITT Population – patients with baseline nail involvement (NAPSI baseline score >0)
- PSSI: based on ITT Population – patients with baseline scalp involvement (PSSI baseline score >0)
- PPASI: based on ITT Population – patients with baseline palmoplantar involvement (PPASI baseline score >0)
- Binary questions on psoriasis locations

The other secondary analyses are detailed in [Table RHCD.6.4](#). Comparisons of ixekizumab versus placebo at Week 12 and all other postbaseline visits will be provided.

Efficacy measures PASI 75, PASI 90, PASI 100, sPGA (0,1), and sPGA (0) at Week 24 and Week 48 will be summarized based on the ITT Population. The immunogenicity impact on efficacy is described in Section [6.14.11.2.2](#).

Protocol Addendum IIF-MC-RHCD(2)

The other secondary efficacy variables include:

- Period 2: ITT Population – Etanercept-Approved Countries
 - PASI50, PASI75, PASI90 and PASI100
 - sPGA (0,1) and sPGA (0)
- Double-Blind Randomized Withdrawal Period (Period 4): Randomized Withdrawal Population
 - Time to relapse to moderate severity (sPGA \geq 2) during the Double-Blind, Randomized Withdrawal Period
 - sPGA(0,1) and sPGA (0)
 - PASI 50, PASI 75, PASI 90 and PASI 100

The other secondary analyses are detailed in [Table RHCD.6.4](#). Analysis methods are detailed in Section [6.1.3.1](#).

6.12. Health-Outcome/Quality-of-Life Analyses

The health-outcome and quality-of-life (QOL) measures are Itch NRS, CDLQI/DLQI, and Patient's global assessment of disease severity. [Table RHCD.6.5](#) and [Table RHCD.6.6](#) include the description and derivation of the health-outcome and QOL measures. There will be no adjustment for multiple comparisons.

The analyses of health-outcome variables for Period 2 will be based on the ITT Population, except:

- Itch NRS ≥ 4 improvement from baseline: based on ITT Population - patients with baseline Itch NRS score ≥ 4

[Table RHCD.6.6](#) provides the detailed analyses including analysis type, method and imputation, population, time point, and dosing regimen comparisons for health-outcome and QOL analyses.

Table RHCD.6.5. Description and Derivation of Health-Outcome and Quality-of-Life Measures

Measure	Description	Variable	Derivation / Comment	Imputation Approach if with Missing Components
Itch NRS	Itch Numeric Rating Scale (NRS): is a single-item, patient-reported outcome (PRO) measure designed to capture information on the overall severity of a patient’s itching due to his/her psoriatic skin condition by having the patient circle the integer that best describes the worst level of itching in the past 24 hours on an 11-point NRS anchored at 0 representing “no itching” and 10 representing “worst itch imaginable.”	Itch NRS score	Range from 0 to 10.	Single item, missing if missing
		Itch NRS change from baseline	Calculated as: observed Itch NRS – baseline Itch NRS	Missing if baseline or observed value is missing
		Itch NRS ≥4 improvement from baseline	Reduced/decreased of ≥4 point from baseline	Missing if baseline or observed value is missing
		Itch NRS = 0	Defined as a postbaseline Itch NRS score of 0	Missing if Itch NRS score is missing
DLQI	Dermatology Life Quality Index (DLQI): is a validated, dermatology-specific, patient-reported measure that evaluates patient’s health-related quality of life. This questionnaire has 10 items that are grouped in 6 domains, including symptoms and feelings, daily activities, leisure, work and school, personal relationships, and treatment. The recall period of this scale is over the “last week.” Response categories and corresponding scores are: Very much = 3 A lot = 2 A little = 1 Not at all = 0 Not relevant = 0	DLQI symptoms and feelings domain	Sum of responses of questions #1 and #2: #1. How itchy, sore, painful or stinging has your skin been? #2. How embarrassed or self-conscious have you been because of your skin?	If one question in a domain is missing, that domain is missing.
		DLQI daily activities domain	Sum of responses of questions #3 and #4: #3. How much has your skin interfered with you going shopping or looking after your home or garden? #4. How much has your skin influenced the clothes you wear?	If one question in a domain is missing, that domain is missing.
		DLQI leisure domain	Sum of responses of questions #5 and #6: #5. How much has your skin affected any social or leisure activities? #6. How much has your skin make it difficult for you to do any sport?	If one question in a domain is missing, that domain is missing.
		DLQI work and school domain	Sum of responses of questions question #7A and #7B: #7A. Has your skin prevented you from working or studying? #7B. If No: how much has your skin been	If the answer to question #7A is missing, this domain is missing. If #7A is No, and #7B is missing, this domain is missing.

Measure	Description	Variable	Derivation / Comment	Imputation Approach if with Missing Components
			a problem at work or studying?	
		DLQI personal and relationships domain	Sum of responses of questions #8 and #9: #8. How much has your skin created problems with your partner or any of your close friends or relatives? #9. How much has your skin caused any sexual difficulties?	If 1 question in a domain is missing, that domain is missing.
		DLQI treatment	Response of question #10: #10. How much of a problem has the treatment for your skin been, for example by making your home messy, or by taking up time?	If 1 question in a domain is missing, that domain is missing.
		DLQI total score	A DLQI total score is calculated by summing all 10 question responses, and has a range of 0 to 30 (less to more impairment) (Finlay and Khan 1994; Basra et al. 2008).	If 2 or more questions are missing, the total score is missing. Note: #7B could be a valid missing while #7A is not “No.” That is, #7 should be considered as 1 question.
		DLQI (0,1)	A DLQI (0,1) response is defined as a postbaseline DLQI total score of 0 or 1. A DLQI total score of 0 to 1 is considered as having no effect on a patient’s health-related quality of life (HRQoL) (Khilji et al. 2002; Hongbo et al. 2005).	Missing if DLQI total score is missing
CDLQI	Children’s Dermatology Life Quality Index (CDLQI): is designed for use in children (subjects form age 4 to age 16 years) (Lewis-Jones and Finlay 1995; Waters et al. 2010; Salek et al. 2013). It consists of 10 items, of which there are 6 headings, including symptoms and feelings, leisure, school or holidays, personal relationships, sleep, and treatment. The recall period of this scale is	CDLQI symptoms and feelings domain	Sum of responses of questions #1 and #2: #1. How itchy, “scratchy,” sore, or painful has your skin been? #2. How embarrassed or self-conscious, have you been because of your skin?	If 1 question in a domain is missing, that domain is missing.
		CDLQI leisure	Sum of responses of questions #4, #5, and #6: #4. How much have you changed or worn different or special clothes/shoes because	If 1 question in a domain is missing, that domain is missing.

Measure	Description	Variable	Derivation / Comment	Imputation Approach if with Missing Components
	over the “last week.” Response categories and corresponding scores are: 0-1 = no effect on child’s life 2-6 = small effect 7-12 = moderate effect 13-18 = very large effect 19-30 = extremely large effect		of your skin? #5. How much has your skin trouble affected going out, playing, or doing hobbies? #6. How much have you avoided swimming or other sports because of your skin trouble?	
		CDLQI school or holidays	Response of question #7A or #7B: #7A. If school time, how much did your skin problem affect your school work? #7B. If holiday time, how much has your skin problem interfered with your enjoyment of the holiday?	If 1 question in a domain is missing, that domain is missing. If both parts of Question 7 are answered, the higher of the 2 scores should be counted.
		CDLQI personal relationships	Sum of responses of questions #3 and #8: #3. How much has your skin affected your friendships? #8. How much trouble have you had because of your skin with other people calling you names, teasing, bullying, asking questions, or avoiding you?	If 1 question in a domain is missing, that domain is missing.
		CDLQI sleep	Response of question #9: #9. How much has your sleep been affected by your skin problem?	If 1 question in a domain is missing, that domain is missing.
		CDLQI treatment	Response of question #10: #10. How much of a problem has the treatment for your skin been?	If 1 question in a domain is missing, that domain is missing.
		CDLQI total score	A CDLQI total score is calculated by summing all 10 question responses, and has a range of 0 to 30 (less to more impairment) (Lewis-Jones and Finlay 1995; Basra et al. 2008).	If 2 or more questions are missing, the total score is missing.

Measure	Description	Variable	Derivation / Comment	Imputation Approach if with Missing Components
		CDLQI (0,1)	A CDLQI (0,1) response is defined as a postbaseline CDLQI total score of 0 or 1.	Missing if CDLQI total score is missing
Patient's Global Assessment of Disease Severity	Patient's Global Assessment of Disease Severity (PatGA): is a subject-administered single-item scale on which subjects are asked to rank by circling a number on a 0 to 5 numerical rating scale (NRS) the severity of their psoriasis today from 0 (clear) = no psoriasis to 5 (severe) = the worst their psoriasis has ever been.	PatGA (0,1)	A PatGA (0,1) response is defined as a postbaseline PatGA score of 0 or 1.	Missing if the item is missing
		Change from baseline	Calculated as: observed PatGA – baseline PatGA	Missing if baseline or observed value is missing

Table RHCD.6.6. Description of Health-Outcomes and Quality-of-Life Analyses

Measure	Variable	Analysis (Method)	Population	Comparison/Time Point
Itch NRS	Itch NRS ≥ 4 improvement from baseline (Gated secondary)	Fisher’s exact test with NRI Logistic regression with NRI	ITT Population – patients with baseline value ≥ 4	Ixekizumab Q4W vs. placebo at Week 12 and all other postbaseline visits during Period 2
	Change from baseline	MMRM	ITT Population	Ixekizumab Q4W vs. placebo at Week 12 and all other postbaseline visits during Period 2
		ANCOVA with LOCF	ITT Population	Ixekizumab Q4W vs. placebo at Week 12 and all other postbaseline visits during Period 2
CDLQI/DLQI	CDLQI/DLQI (0,1)	Fisher’s exact test with NRI Logistic regression with NRI	ITT Population	Ixekizumab Q4W vs. placebo at Week 12 and all other postbaseline visits during Period 2
PatGA	PatGA (0,1)	Fisher’s exact test with NRI Logistic regression with NRI	ITT Population	Ixekizumab Q4W vs. placebo at Week 12 and all other postbaseline visits during Period 2
	Change from baseline	ANCOVA with LOCF	ITT Population	Ixekizumab Q4W vs. placebo at Week 12 and all other postbaseline visits during Period 2

Abbreviations: ANCOVA = analysis of covariance; CDLQI = Children’s Dermatology Life Quality Index; DLQI = Dermatology Life Quality Index; ITT = intent-to-treat; LOCF = last observation carried forward; MMRM = mixed-effects model of repeated measures; NRI = nonresponder imputation; NRS = Numeric Rating Scale; PatGA = Patient’s Global Assessment of Disease Severity; Q4W = every 4 weeks; vs. = versus.

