6.1.3. Analysis Methods

6.1.3.1. Double-Blind Treatment Period (Period 2): Main Protocol

The primary analysis method for categorical data for treatment group comparisons will be Fisher's exact test. The difference of the proportions and the 95% CI of the difference will be included.

Secondary analyses for the primary efficacy measures, PASI 75 and sPGA(0,1), and other categorical efficacy and health outcome measures, will be conducted using a logistic regression analysis with treatment group, region, baseline sPGA score (severity of Ps), and baseline weight category (<25 kg, ≥25 to ≤50 kg, or >50 kg) as factors. The odds ratio and the corresponding 95% CI will be reported.

The analyses for the continuous efficacy and health-outcome variables will be made using analysis of covariance (ANCOVA) and mixed model for repeated measures (MMRM) analysis. The ANCOVA model includes treatment group, region, baseline sPGA score, baseline weight category, and baseline value. Type III sums of squares for the least-squares means will be used for the statistical comparison; the 95% CI will be reported.

When the MMRM is used, the model will include treatment, region, baseline sPGA score, baseline weight category, baseline value, visit, treatment-by-visit, and baseline-by-visit interactions as fixed factors. The covariance structure to model the within-subject errors will be unstructured. The Kenward-Roger method will be used to estimate the denominator degrees of freedom. Type III tests for the least-squares means will be used for the statistical comparison; the 95% CI will be reported. Treatment comparisons at Week 12 and all other postbaseline visits will be reported.

If the unstructured covariance matrix results in a lack of convergence, the heterogeneous Toeplitz covariance structure, followed by the heterogeneous autoregressive covariance structure, followed by the compound symmetry will be used. This order is specified according to a decreasing number of covariance parameters in the structure. The sandwich estimator (Diggle et al. 1994) for the covariance estimation will be used by specifying the EMPIRICAL option in SAS PROC MIXED. When sandwich estimation is used, the Kenward-Roger approximation for denominator degrees of freedom cannot be used. Instead, the DDFM= BETWITHIN option will be used to estimate denominator degrees of freedom.

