6.16. Protocol Deviations

Protocol deviations will be identified throughout the study. Important protocol deviations are defined as those deviations from the protocol likely to have a significant impact on the completeness, accuracy, and/or reliability of the study data, or that may significantly affect subject's rights, safety, or well-being.

The major protocol deviations, which are the subset of the important protocol deviations, are the protocol deviations that might have impact on the efficacy and/or safety results. The impact of major protocol deviations on the efficacy results will be investigated by assessing the robustness of the study results and conclusions to the choice of analysis population, both by including and excluding the data potentially affected by major protocol deviations. As specified in Section 6.1.1, the PPS Population is defined as all randomized patients who do not have major protocol deviations.

Table RHCD.6.12 includes the categories and subcategories of important protocol deviations, whether or not these deviations are major protocol violations, the action to be taken regarding the exclusion of patients from PPS, the source of the deviation identified, and the statistical programming guidance for the clinical study report (CSR).

The number and percentage of patients having important protocol deviation(s) will be summarized within category and subcategory of deviations by treatment group for the ITT Population for the Double-Blind Treatment Period (Period 2).

A by-patient listing of important protocol deviations will be provided.

Table RHCD.6.12. Identification and Action of Important Protocol Deviations

Important Protocol Deviation Category/Subcategory/Study Specific	Action for PPS Analysis	Source to Identify Protocol Deviation ^a	Statistical Programming Guidance for Clinical Study Report
Category: Eligibility			
Subcategory: Inclusion/Exclusion			
[1] No confirmed diagnosis of moderate-to-severe plaque-type Ps for at least 6 months prior to Visit 2	Excluded from PPS	Monitor and Stats	Either from monitor’s list, or, if date of diagnosis of Ps is missing or less than 6 months prior to Visit 2.
[2] PASI score <12 or sPGA <3 or BSA involvement <10% at Visit 1 or Visit 2	Excluded from PPS	Monitor and Stats	Either from monitor’s list, or, If PASI score <12 or sPGA <3 or BSA involvement <10% or any missing at Visit 1 or Visit 2.

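### CDLQI/DLQI (0,1) and PatGA (0,1) count subjects who start and stay at 0 or 1 as responders, and the logistic model omits the measure's own baseline score

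*SAP*

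**What the plan says.** Table RHCD.6.5 in SAP Section 6.12 gives three response definitions of the same form:

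- CDLQI: "A CDLQI (0,1) response is defined as a postbaseline CDLQI total score of 0 or 1".
- DLQI: "A DLQI (0,1) response is defined as a postbaseline DLQI total score of 0 or 1".
- PatGA: "A PatGA (0,1) response is defined as a postbaseline PatGA score of 0 or 1".

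None has a baseline condition or a minimum change. On the population, Section 6.12 says: "The analyses of health-outcome variables for Period 2 will be based on the ITT Population, except". The single exception that follows is the itch response, confined to "patients with baseline Itch NRS score" of at least 4. Table RHCD.6.6 accordingly lists the plain ITT Population for CDLQI/DLQI (0,1) and PatGA (0,1), each analysed by Fisher's exact test and by logistic regression with nonresponder imputation.

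The severity criteria in SAP Section 5.1 concern PASI, sPGA and BSA. The matching eligibility deviation in Table RHCD.6.12 names the same three: "PASI score <12 or sPGA <3 or BSA involvement <10% at Visit 1 or Visit 2". No minimum for CDLQI, DLQI or PatGA is stated. Section 6.8.1 tabulates baseline PatGA in categories that include 0 and 1.

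Section 6.1.3.1 specifies a "logistic regression analysis with treatment group, region, baseline sPGA score (severity of Ps), and baseline weight category" as factors. In the same section, the ANCOVA and MMRM models for continuous outcomes include the baseline value of the outcome.

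**The concern.** A response of 0 or 1 reads most naturally as something a subject reaches on treatment. As defined, it also includes subjects who were there at randomization and did not move. They raise the reported response rate in both arms without showing any improvement.

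sPGA (0,1) has the same absolute form, but entry at sPGA 3 or more means nobody can start as a responder. Other clearance endpoints are confined to subjects with something to clear; scalp, for example, uses "patients with baseline scalp involvement (PSSI baseline score >0". CDLQI/DLQI (0,1) and PatGA (0,1) have neither safeguard.

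The adjusted analysis could absorb baseline differences on the measure, but its covariates are baseline sPGA and weight category, not the score being analysed. For CDLQI/DLQI this matters a little more: Table RHCD.6.6 lists no change-from-baseline analysis, so (0,1) is the only planned between-arm comparison of quality of life. PatGA does have a change-from-baseline ANCOVA.

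At stake are the size and reading of the reported rates and risk differences, and some precision in the adjusted model.

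**Working it through.** **Inputs from the documents.** 110 ixekizumab and 55 placebo subjects, with a 2-sided Fisher exact test at 0.05 (SAP Section 5.2.1). Planning rates of 80% vs 10% are given for PASI 75 and sPGA (0,1) only. Nothing is given for CDLQI/DLQI (0,1) or PatGA (0,1).

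**The plan's own figure.** Exact Fisher power at 110 vs 55 and 80% vs 10% is about 100%, which agrees with the stated >99%. It concerns the co-primary endpoints and serves only to check the method.

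**Validity.** With the same 30% response in both arms, the Fisher test at 110 vs 55 rejects 4.1% of the time. Baseline 0-1 subjects are spread over the arms by randomization, so they create no false difference.

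**Assumed inputs.**

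- f, the share at 0-1 at baseline. As a guide, take negative-binomial CDLQI totals with mean m and SD s, so p = m/s², r = m²/(s² - m), and P(total ≤1) = p^r [1 + r(1 - p)]. For m = 9, s = 5: p = 0.36, r = 5.06, giving 2.4%. For m = 7, s = 7: p = 0.143, r = 1.17, giving 20.7%. I use 2% to 20%. No such guide is available for PatGA.
- d1, the treatment difference among subjects starting at 2 or more. I take 50% vs 25%, so d1 = 25 points.
- d0, the treatment difference among subjects starting at 0-1.

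**Formula.** ITT difference = (1 - f) × d1 + f × d0.

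**Case A: everyone at 0-1 stays there in both arms (d0 = 0).** The difference becomes (1 - f) × 25.

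| f | ITT difference (points) | Fisher power, full ITT | Fisher power, baseline >1 only |
|---|---|---|---|
| 0% | 25.0 | 88.4% | 88.4% |
| 2% | 24.5 | 86.8% | 87.5% |
| 5% | 23.8 | 84.0% | 85.4% |
| 10% | 22.5 | 78.5% | 82.1% |
| 20% | 20.0 | 65.8% | 77.4% |

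The rates themselves rise. At f = 10%, placebo reads 0.90 × 25 + 10 = 32.5% instead of 25%, and ixekizumab 0.90 × 50 + 10 = 55% instead of 50%.

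With 80% vs 10% in place of 50% vs 25%, f = 10% takes 70.0 points to 0.90 × 70 = 63.0, and power stays at about 100%.

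**Case B: 95% stay on ixekizumab and 70% on placebo (d0 = 25).** At f = 10%: 0.90 × 25 + 0.10 × 25 = 25.0 points, unchanged. Power is 87.1% in full ITT and 82.1% with the restriction.

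**Case C: 95% stay on ixekizumab and 50% on placebo (d0 = 45).** At f = 10%: 0.90 × 25 + 0.10 × 45 = 27.0 points, a rise. With 80% vs 10% the same retention gives 0.90 × 70 + 0.10 × 45 = 67.5 points, a fall.

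The direction therefore turns on whether d0 is below or above d1, and the documents fix neither.

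**The case against.** The strongest reply is that these are attained-state endpoints. Table RHCD.6.5 describes a DLQI total of 0 to 1 as no effect on quality of life, and the share of all randomized subjects in that state at Week 12 is a legitimate quantity. That stands, and it is why the full-ITT analysis should be kept.

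A reader might infer that the treatment difference is bound to be diluted, by about the share at 0-1. The documents do not support that. It requires equal retention of 0-1 scores in both arms. In a simulation with no treatment effect (negative-binomial totals with mean/SD 7/5, 8/6, 9/6 and 9/7, correlation 0.70 to 0.85), only 39% to 61% of subjects starting at 0-1 were still there later. Placebo subjects may lose the state, and treatment can then separate the arms within this group.

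A reader might also infer that every comparable endpoint is restricted and these were overlooked. That is too strong. The itch response is a fall of 4 points, which is impossible from a baseline below 4. PPASI percentage improvement divides by the baseline score. NAPSI, PSSI and PPASI are used only where that involvement exists at baseline. These restrictions are largely structural.

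Finally, Section 3 of the SAP says this version was approved after the primary database lock, and Section 6.17 places the final Period 2 analysis at the Week 12 lock and unblinding. Replacing the population now would be a post-hoc change. That also stands. None of this explains why the logistic model leaves out the measure's own baseline score.

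**Conclusion.** The point holds in a limited form. Subjects who start at 0-1 and remain there count as responders in both arms, and the logistic model ignores the baseline score that identifies them. The test is valid under the null.

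Under equal retention, an assumed 25-point difference falls to between 24.5 points (f = 2%) and 20.0 points (f = 20%). Under unequal retention it may be unchanged or may rise. The values of f, the 50% vs 25% rates and the retention rates are all assumptions; neither the size nor the direction can be read from the documents.

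Severity is minor. Both endpoints are other secondary endpoints, outside the gated sequence in Section 6.5 and not adjusted for multiplicity. No co-primary or gated endpoint is affected.

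**What to change.** 1. In SAP Section 6.1.3.1 and Table RHCD.6.6, add the baseline score of the measure to its logistic regression. For CDLQI/DLQI, also add an indicator of the instrument used, since Section 6.18.1.3.1 assigns CDLQI to ages 6-16 and DLQI to those over 16.
2. Keep the full-ITT Fisher analysis with nonresponder imputation as planned.
3. Add a supplementary analysis of each endpoint in ITT subjects with baseline score >1, and report the share at 0-1 at baseline by arm.
4. If these enter the present SAP version, label them as added after the primary database lock.

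Baseline scores are already collected. The cost is a few table rows, slightly fewer subjects in the supplementary analysis, and the loss from the adjusted model of any subject with a missing baseline score.

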6.5. Multiple Comparisons/Multiplicity

A multiple testing strategy for the primary and major secondary objectives will be implemented to control the family-wise type I error rate at a 2-sided α level of 0.05. The primary and key secondary comparisons will be tested by using the primary analysis method, Fisher's exact test, with an NRI missing-data imputation approach.

A gatekeeping approach will be used for multiple comparisons to control the family-wise error rate. To assess whether ixekizumab Q4W is superior to placebo, the following endpoints will be tested:

- Primary 1: Proportion of subjects achieving PASI 75 at Week 12
- Primary 2: Proportion of subjects achieving sPGA (0,1) at Week 12
- Secondary 1: Proportion of subjects achieving PASI 90 at Week 12
- Secondary 2: Proportion of subjects achieving sPGA (0) at Week 12
- Secondary 3: Proportion of subjects achieving PASI 100 at Week 12
- Secondary 4: Proportion of subjects achieving ≥ 4 point improvement for subjects who had a baseline Itch numeric rating scale (NRS) ≥ 4 at Week 12
- Secondary 5: Proportion of subjects achieving PASI 75 at Week 4
- Secondary 6: Proportion of subjects achieving sPGA (0,1) at Week 4

The Primary 1 will first be tested at 2-sided $\alpha=0.05$. If successful, the test for Primary 2 will be performed at 2-sided $\alpha=0.05$. Otherwise, the test will stop. If the Primary 2 endpoint is successful, the Secondary 1 endpoint will be tested. The test will continue to the last endpoint if all the prior tests are successful. If a test is not successful, all subsequent tests will not be tested.

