6.18.1.3. Construct Validity

6.18.1.3.1. Convergent and Discriminant Validity

Construct validity is the degree to which a measure is related to other measures or constructed in a manner that is consistent with theory. *Convergent validity* involves demonstrating that different measures of the same concept substantially correlate, while *discriminant validity* demonstrates that concepts that are supposed to be unrelated are, in fact, unrelated.

Convergent validity will be assessed by Pearson correlations and Spearman rank-based correlation coefficient at baseline and at Week 12 between scores of the Itch NRS and other assessments, including PASI, sPGA, PatGA, DLQI (assessed in patients aged >16 years), and CDLQI (assessed in patients aged 6-16 years).

Cohen's conventions will be used to interpret the absolute value of the correlation results, where a correlation >0.5 is large, 0.3 to ≤0.5 is moderate, 0.1 to <0.3 is small, and <0.1 is insubstantial (Cohen 1988). It is hypothesized that small-to-moderate correlations at baseline and moderate-to-large (≥0.30) correlations at Week 12 are expected between the Itch NRS and PASI, sPGA, PatGA, and DLQI / CDLQI total scores.

Additionally, convergent and discriminant validity will be assessed by Pearson correlation and Spearman rank-based correlation at baseline and at Week 12 between scores of the Itch NRS and the DLQI / CDLQI 6 domains: Symptoms and Feelings, Daily Activities, Leisure, Work and School, Personal Relationships, and Treatment (note the CDLQI domains are Symptoms and Feelings, Sleep, Leisure, School or Holidays, Personal Relationships, and Treatment). It is hypothesized that the Itch NRS will correlate higher with the DLQI / CDLQI Symptoms and Feelings domain than with the other 5 DLQI domains.

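### The secondary logistic regression for the Itch NRS responder endpoint leaves out baseline Itch NRS, which may cost some precision if baseline itch is prognostic; the gated Fisher test is not affected

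*SAP*

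**What the plan says.** - **Endpoint.** SAP Table RHCD.6.5 describes the Itch NRS as "Range from 0 to 10" and defines response as a reduction of 4 or more points from baseline. Table RHCD.6.6 restricts the analysis to ITT subjects with a baseline score of at least 4 and marks the row "improvement from baseline (Gated secondary".
- **Gated test.** Section 6.5: "The primary and key secondary comparisons will be tested by using the primary analysis method, Fisher's exact test", with nonresponder imputation. Section 6.11.2 repeats this for the gated secondary endpoints and names no adjusted model.
- **Adjusted model.** Section 6.1.3.1 says that secondary analyses of the co-primaries "and other categorical efficacy and health outcome measures, will be conducted using a logistic regression analysis". Its terms are those of a "logistic regression analysis with treatment group, region, baseline sPGA score (severity of Ps), and baseline weight category". Table RHCD.6.6 lists this regression for the itch responder row and adds no covariate.
- **Baseline value elsewhere.** Sections 6.1.3.1 and 6.2 put the baseline value in the ANCOVA and MMRM, which Table RHCD.6.6 uses for itch change from baseline. Section 6.2 makes no such provision for logistic regression.
- **sPGA as a proxy.** In Section 6.18.1.3.1, on the Itch NRS against sPGA and other measures: "It is hypothesized that small-to-moderate correlations at baseline".
- **Timing.** The Revision History (Section 3) shows the logistic regression entering Table RHCD.6.6 after Version 1, as a secondary method. Version 3 was approved after the primary database lock.

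**The concern.** A fixed 4-point fall makes the score a subject must reach depend directly on where that subject started. Among the categorical endpoints in Tables RHCD.6.4 and RHCD.6.6, this is the only one defined by a fixed-point fall. The others use percent improvement, an end state such as a score of 0 or 0/1, or absence of psoriasis at a site. The common covariate list includes sPGA, and so gives the sPGA responder model its own baseline. It does not do this for itch, and the SAP expects sPGA to track itch only loosely at baseline.

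What is at stake is the quality of one supporting odds ratio. If baseline itch predicts response, a model without it has less power for the treatment effect. It also cannot answer the question a reader will ask if the baseline table shows the arms differing in itch. Randomisation is not stratified by itch.

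**Working it through.** **1. Score needed to respond.** Response requires baseline minus follow-up ≥ 4, so the highest qualifying follow-up score is baseline − 4: 4 → 0, 7 → 3, 10 → 6.

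**2. The plan's own figure.** SAP 5.2.1 gives 110 v 55 subjects, 80% v 10% response and a two-sided Fisher test at 0.05, with stated power above 99%. Exact enumeration gives 1.000, so the figure reproduces. It concerns PASI 75 and sPGA (0,1). The SAP gives no response rates or power for itch.

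**3. Assumed itch analysis set.** The documents do not give the share with baseline ≥ 4. Taking 75%: 110 × 0.75 ≈ 82 and 55 × 0.75 ≈ 41. Shares of 60% to 90% give 66 v 33 to 99 v 50. Over that range Fisher power is 1.000 at 80% v 10%, 0.971 to 0.998 at 60% v 20%, and 0.830 to 0.948 at 50% v 20%. None of these depends on the covariate list.

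**4. Power of the logistic Wald test without → with baseline Itch NRS.** 82 v 41, 1,500 simulated trials per cell. Assumed: baseline scores spread over 4 to 10 (SD 1.83); a baseline odds ratio (OR) per itch point as shown; other covariates not prognostic.

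| Response rates | OR 1.0 | OR 1.2 | OR 1.5 | OR 2.0 |
|---|---|---|---|---|
| 80% v 10% | 0.991 → 0.991 | 0.985 → 0.985 | 0.990 → 0.990 | 0.985 → 0.985 |
| 60% v 20% | 0.993 → 0.993 | 0.993 → 0.995 | 0.989 → 0.993 | 0.990 → 1.000 |
| 50% v 20% | 0.919 → 0.920 | 0.910 → 0.911 | 0.919 → 0.939 | 0.907 → 0.958 |
| 45% v 20% | 0.791 → 0.791 | 0.796 → 0.805 | 0.809 → 0.838 | 0.802 → 0.893 |

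At ORs of 1.5 and 2.0 the gains are 2.0 and 5.1 points at 50% v 20%, and 2.9 and 9.1 points at 45% v 20%. In the top row, power falls short of 1 because the Wald test fails when very few placebo subjects respond. That happens equally in both models.

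**5. Chance imbalance.** The SE of the arm difference in mean baseline itch is 1.83 × √(1/82 + 1/41) = 0.35, so 95% of trials fall within 1.96 × 0.35 = 0.69 point. The shift in one arm's response rate at that limit is about ln(OR) × 0.69 × p(1 − p). For p = 20% to 50% this is 2 to 3 percentage points at OR 1.2, 4.5 to 7 at 1.5, and 8 to 12 at 2.0. These are upper figures, since sPGA would absorb part.

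**6. Type I error.** Over all trials, the model without baseline itch rejects a true null 4.6% to 4.9% of the time. A second null simulation used 40,000 trials per OR, about 30% response at mean baseline itch, and sPGA in both models with itch–sPGA correlation about 0.35. About 15% of trials had an itch difference above 0.5 point. Within those, rejection without v with baseline itch was 5.8% v 5.7% (OR 1.2), 7.7% v 5.0% (1.5) and 9.9% v 4.3% (2.0).

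**7. Shift in the estimate.** At 50% v 20% and OR 1.5, the median log odds ratio is 1.45 without and 1.62 with the term. The true marginal value is ln(0.5/0.5) − ln(0.2/0.8) = 1.39 and the true value conditional on itch is 1.55. The estimates differ by 0.17 and their targets by 0.16, so nearly all the shift is a change of quantity.

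**The case against.** The strongest reply is that nothing decisive depends on this model. The gate is decided by unadjusted Fisher, and the logistic regression carries no alpha. One covariate list for every categorical endpoint is a defensible simplification: CDLQI/DLQI (0,1), PatGA (0,1) and nail and scalp clearance also omit their own baselines. Baseline itch is tabulated by arm with between-group comparisons (Section 6.8.1), and itch change is already analysed with baseline adjustment. More room to fall does not prove that baseline itch is prognostic, and the documents give no estimate of that.

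Most of this stands, and it limits the point to a minor one. Two parts do not fully answer it. The baseline table covers the whole ITT Population, so it shows an imbalance without adjusting for it. The ANCOVA and MMRM are on the continuous scale and are not restricted to subjects with baseline ≥ 4, so they do not adjust the responder odds ratio.

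A reader might infer more than the documents support:
- **That the gated itch test is weakened.** It uses no covariates, so it is not.
- **That the trial loses power.** The loss needs a prognostic baseline and a moderate effect, neither of which is documented.
- **That baseline itch is the strongest predictor of response, or that this odds ratio bears on labelling.** Neither claim appears in the documents.
- **That the move from 1.45 to 1.62 is corrected bias.** It is almost entirely non-collapsibility of the odds ratio.

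**Conclusion.** The omission is real, confined to a secondary analysis, and small. The itch responder regression lacks the one baseline score that sets its own response threshold, while the itch-change models include theirs.

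The cost depends on inputs the documents do not give: itch response rates, the share and spread of baseline scores of 4 or more, and the strength of the baseline relation. It is nil at 80% v 10%, which are the plan's rates for PASI 75 and sPGA, and nil or nearly so if baseline itch is not prognostic. It reaches about 3 to 9 points of power only with a weaker effect and a strong relation. Overall type I error holds. The more practical gain is protection when the arms happen to differ in baseline itch, and that too appears only at ORs of about 1.5 per point or more.

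**What to change.** In SAP 6.1.3.1 and Table RHCD.6.6, add baseline Itch NRS score as a continuous covariate to the logistic regression for Itch NRS improvement of at least 4 points. Leave the gated Fisher test and the nonresponder imputation as they are.

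Costs:
- **Model size.** One further parameter. The score is already collected, and the analysis set requires a baseline value of at least 4, so no subject is lost for a missing covariate.
- **Interpretation.** The odds ratio becomes conditional on baseline itch and will tend to lie further from 1. Report it beside the prespecified one, with a note that the two are different quantities.
- **Timing.** Version 3 follows the primary lock, which under Section 6.17 includes unblinding and the final Period 2 analysis. The Week 12 result, and those for the earlier Period 2 visits locked with it, should be labelled post hoc sensitivity analyses.
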